11.5.3 Definition of Heart Failure Hospitalization

Hospitalization for worsening heart failure is defined as a hospitalization that includes increased signs and/or symptoms of worsening heart failure requiring the administration or augmentation of intravenous or oral heart failure therapy (e.g., inotropes, diuretics, and/or vasodilators).

A hospitalization classification will be based on the primary admission diagnosis, not on the development of new events that occur during the hospitalization.

For each hospital admission, the investigator will be requested to state whether or not the subject experienced worsening heart failure at the time of admission or during the admission, and if so, whether or not this was the primary reason for admission or secondary to an obvious precipitating factor such as atrial fibrillation. The investigator will also be asked to state whether or not the subject received an intravenous medication for heart failure including diuretics, vasodilators or inotropic agents or a substantial increase in oral diuretic therapy for heart failure.

11.5.4 Adverse Events

In addition to the adverse events reportable for the main QP ExCELS study, Section 6.2, the investigator shall report to the sponsor by completing the appropriate eCRF, the following type of events specific to the MPP sub-study:

- Any cardiovascular hospitalizations and any other hospitalizations in which cardiovascular symptoms occur on or before the date of the 12-Month follow-up^{§§}.
- All adverse events that required additional invasive intervention to resolve, specifically related to the MPP feature of the CRT-D. These adverse events include any software issues related to MPP programming for any adverse event that occurs while MPP is enabled and that may be attributed to the use of the MPP feature.

^{§§} 9-month follow-up for subjects enrolled at the 3-month follow-up.

11.5.5 Adverse Events for Secondary Endpoint Analysis

The AE-free rate calculated for secondary endpoint 1 will be based on the total number of subjects with at least one MPP related adverse event requiring additional invasive intervention to resolve. For the secondary endpoint analysis, the AE classification, category, resolution, and relation to the MPP feature for each individual event will be determined by the Clinical Events Committee (Section 11.3.4)

All adverse events which the CEC determines the event is related or possibly related to the MPP feature will be included in the secondary endpoint event analysis. Adverse events with a final CEC adjudicated relation of not related or unknown will not contribute to or be included in the evaluation of the secondary endpoint.

11.5.6 Consent Materials (MPP Sub-Study)

Prior to the patient's participation in the sub-study, informed patient consent is required from all patients. Informed consent should be obtained in accordance with the FDA regulations (21CFR, Part 50). The investigator is required to inform BIOTRONIK and the reviewing IRB within 5 days if any patient was not appropriately consented to participate in the study. BIOTRONIK is then required to report any failure to obtain patient consent to the FDA within 5 working days of learning of such an event. In order to assist with the consent process, BIOTRONIK will provide a template patient consent form to investigational sites participating in the study.

11.5.7 IRB Approval

Institutional Review Board (IRB) approval is required from each institution prior to participation in this clinical investigation (sub-study). Patient enrollment may not begin until the IRB and BIOTRONIK have granted approval for the investigational site. IRB approval is also required throughout the duration of this clinical investigation. If IRB approval is withdrawn, BIOTRONIK must be notified within 5 working days.

12. JUSTIFICATION FOR THE DESIGN OF THE PRE-MARKET CLINICAL INVESTIGATION

The Sentus QP leads are 4.8 French (F) quadripolar left ventricular leads designed for use with biventricular pacing systems. Sentus QP is the successor of the Corox OTW bipolar (BP) LV leads. The Corox LV leads are market approved in the U.S. and internationally. They have been extensively studied in the ongoing CELESTIAL Post Approval Registry (NCT#00810264). Quadripolar LV leads are relatively new to the market. In the U.S., the first quadripolar LV lead received market approval November 2011 and is currently undergoing evaluation in a post-approval study. A second quadripolar LV lead more recently received approval for the U.S. market.

The results of CELESTIAL, summarized below, along with data collected during the EchoCRT study and available results from competitive quadripolar lead studies were used to support the expected performance goals and design for the pre-market endpoints of this clinical study.

Several clinical investigations conducted by BIOTRONIK Inc. or BIOTRONIK SE & Co. KG were relevant for the design of this clinical investigation:

- EveresT
- CELESTIAL Post Approval Registry
- EchoCRT
- Eluna Family/Sentus BP Master Study
- Iperia Family / Sentus QP Master Study

12.1 EveresT

The clinical study everesT was conducted by BIOTRONIK SE & Co. KG to assess the clinical safety and efficacy of the Corox OTW BP steroid polyurethane coated bipolar left ventricular lead and of Lumax HF-T 300/340 CRT-D devices. Two different fixation types of the Corox BP were investigated: a three dimensional pre-shaped helical tip to achieve a stable position in larger veins (Corox OTW BP) and a straight tip 'wedge position' (Corox OTW-S BP) for placement in smaller veins.

148 subjects in 25 sites from Austria, Germany, Italy, Israel, Switzerland and United Kingdom were enrolled in this prospective, non-randomized investigation. The first implantation was conducted on August 2, 2006 and the analysis consists of clinical data until September 30, 2007.

Summary of results:

- Corox LV lead implantation was attempted in 144 of 148 study subjects (97%)
- 131 of the attempted Corox implants were successful (91%)
- Implantation efficacy of Corox OTW BP helix was 91.5% (89/97)

- Implantation efficacy of Corox OTW-S BP straight was 89.5% (30/34)
- Out of 131 study subjects with a successful Corox implantation, a total of 2 Corox BP LV lead related complications were seen in 2 subjects within 90 days post implantation
- 1.5% of the study subjects with a successful Corox BP implantation experienced an LV lead related complication at 3 months post implantation (lead dislodgement, loss of capture)
- One Lumax HF-T device related complication occurred due to a pocket infection
- Corox BP LV lead measurements demonstrated good results in known ranges at implantation, pre-hospital discharge/wound check, and 1-, 3- and 6- month follow-up visits

Table 9 lists the reasons for the 13 unsuccessful Corox BP lead implantations:

Table 12: Reasons for Corox BP Implantation Failure

Reasons for implant failure	N _{Failure} *
Inability to find stable position	6 (46%)
Anatomical difficulties	5 (38%)
Inability to advance the lead	4 (31%)
Lead dislodged while removing guide catheter	4 (31%)
High threshold	3 (23%)
Dissection of coronary sinus	1 (8%)
Phrenic nerve stimulation	1 (8%)
No reason given	1 (8%)
Total Corox BP implant failures	13

*Percentages total over 100% because multiple answers could be given for reason of implant failure.

The data received and analyzed during the evereT clinical study demonstrate the safety and efficacy of the Lumax HF-T CRT-D device and Corox OTW (-S) BP Steroid.

12.2 CELESTIAL Study: Clinical Experience with Corox LV Lead

BIOTRONIK, Inc. is currently conducting the CELESTIAL post-approval study (P070008) to confirm the long-term safety and reliability of the Corox OTW BP LV leads. This multi-center, prospective, non-randomized registry has been ongoing since December 2008 with enrollment of 2,499 subjects completed on October 16, 2013. As of the May 2014 bi-annual report, the cumulative follow-up duration was 5,741 years (mean duration 2.3 years).

Data from the May 2014 bi-annual report is summarized below. In one column, results from all three Corox LV lead models included in the CELESTIAL Study (OTW, OTW-S, and OTW-L) are provided, as the materials and lead body design are similar to Sentus QP. In a separate column, data from the Corox OTW-L and OTW-S leads are presented as these lead tip shapes are similar to those leads included in this study.

The CELESTIAL Study permits enrollment up to 180 days post-implant and the visit schedule permits 3, 4, or 6 month visit intervals depending on the investigator's standard of care for CRT subjects. The complication-free rate at 6 months was calculated using the implant date and any qualifying adverse events occurring within 6 months post-implant. Lead measurements are from the actual 3 month evaluation; therefore, the number of subjects is less than the total study population.

Table 13: CELESTIAL Study Supporting Data

	All Corox models	Corox OTW-L and Corox OTW-S
Data supporting safety endpoint		
Subjects with safety data through 6 months post-implant, n	2,128	1,520
Corox related complication-free rate at 6 months post-implant*	97.4%	97.6%
Total subjects with Corox related complication, n (%)	56 (2.6%)	37 (2.4%)
Lead dislodgement	35 (1.6%)	21 (1.4%)
Diaphragmatic/pectoral stimulation	13 (0.6%)	10 (0.7%)
High pacing threshold/intermittent or no capture	7 (0.3%)	5 (0.3%)
Lead impedance out of range. Potential conductor fracture.	1 (0.0%)	1 (0.1%)
Procedure-related events	0 (0.0%)	0 (0.0%)
Data supporting efficacy endpoint		
Subjects with efficacy data at 3 months post-implant, n	1,475	1,095
Elevated threshold† free rate at 3 months post-implant	93.2%	93.0%
Total subjects with elevated threshold, n (%)	101 (6.8%)	77 (7.0%)
Corox lead performance at 3 months post-implant		
R-wave sensing, mean (±SD) in mV	13.6 (±7.3)	13.5 (±7.3)
Pacing threshold, mean at 0.5 ms (±SD) in V	1.4 (±1.1)	1.4 (±1.1)
Impedance, mean (±SD) in ohms	732 (±251)	730 (±248)

*Includes all Corox related events resolved with an invasive action or for which the lead was abandoned, continued to be used despite a known clinical performance issue, or when polarity or mode reprogramming was utilized for suspected lead failures. In addition, procedure-related events

(such as cardiac perforation, pneumothorax, and coronary sinus dissection) that were directly caused by the LV lead were included.

†Elevated threshold is defined as an LV pacing threshold > 3.5 V in any standard bipolar pacing vector.

12.3 Complication-free Rate in the EchoCRT Trial

To further refine the expected complication-free rate, adverse events collected as part of the EchoCRT trial (IDE# G080067) were evaluated. The EchoCRT trial was a randomized control trial conducted at 115 sites in 17 different countries conducted by BIOTRONIK, Inc. At study termination, 821 narrow QRS subjects had been implanted with a CRT-D system (mean implant duration of 1.7 years). Though the LV leads implanted in EchoCRT were not exclusively manufactured by BIOTRONIK, the data is informative because subjects were consented prior to implant, which limits subject selection bias and ensures reporting of all adverse events that occur at or immediately after device implant.

Table 14: EchoCRT Supporting Data

Data supporting safety endpoint	All LV leads
Subjects with safety data through 6 months post-randomization, n	670
LV lead related complication-free rate at 6 months post-randomization*	94.5%
Total subjects with LV lead related complication, n (%)	37 (5.5%)
Lead dislodgement	24 (4.3%)
Diaphragmatic/pectoral stimulation	4 (0.6%)
High pacing threshold/intermittent or no capture	2 (0.3%)
Procedure-related events	2 (0.3%)

*Includes all LV lead related events resolved with an invasive action or for which the lead was abandoned, continued to be used despite a known clinical performance issue, or when polarity or mode reprogramming was utilized for suspected lead failures, or events in which these actions would have been taken if subject had been randomized to CRT ON treatment arm. In addition, procedure-related events (such as cardiac perforation, pneumothorax, and coronary sinus dissection) that were directly caused by the LV lead were included.

12.4 Eluna Family /Sentus BP Master Study

This Master Study is performed by BIOTRONIK SE & Co. KG to confirm the safety and efficacy of the Eluna pacemaker family and the Sentus BP left ventricular lead. The Sentus BP left ventricular lead is the bipolar model of the Sentus leads and is similar in design to the quadripolar QP lead variants. After implantation of the Sentus BP lead, 2 in-hospital follow-ups are part of the study (pre-hospital discharge and 3 months after implantation). The data will be used to support the regulatory process in Japan. The study has enrolled 166 subjects and is currently in the follow-up phase.

12.5 Iperia Family / Sentus QP Master Study

This Master Study is performed by BIOTRONIK SE & Co. KG to confirm the safety and efficacy of the Iperia ICD family. The CRT-D devices of the Iperia Family are implanted in combination with the Sentus QP left ventricular lead. After implantation of the device system, 2 in-hospital follow-ups are part of the study (pre-hospital discharge and 3 months after implantation). The data will be used to support the regulatory process in Japan. The study has enrolled 152 subjects and is currently in the follow-up phase.

12.6 Published Results for Competitive Quadripolar Leads

Tomassoni et al., 2013 evaluated the safety and efficacy of the St. Jude Medical Promote® Q device system (Promote® Q CRT-D and Quartet® LV lead) in a clinical investigation. The CRT-D device is equipped with an IS4 connector to facilitate the implantation of the corresponding LV lead. The Quartet® LV lead is a quadripolar lead and has an over-the-wire design. In total 178 subjects were enrolled in the study. The device system was implanted successfully in 170 subjects (95.5%). The primary safety endpoint was designed to show the freedom from LV lead related complications from implantation to the 3-month post-implantation visit. The complication free rate was calculated to 96%. The 97.5% lower confidence interval of 93% is greater than the success criterion of 85%. The LV capture thresholds and pacing impedances in all 10 vectors remained stable during follow-up. LV lead dislodgment occurred in 6 subjects and phrenic nerve stimulation (PNS) was observed in 23 subjects. PNS was resolved non-invasively in all cases by reprogramming of the device.

Performance criteria and results from this IDE study are presented in Table 15.

Table 15: Competitive Quadripolar LV Lead Performance

	Safety	Efficacy
Performance criteria	85%	75%
Outcome	96% (97.5% LCB = 93%)	79.7% (97.5% LCB = 73%)

Source: Review Memo for P030054-S173 from FDA.gov. Efficacy is from the per protocol analysis (percentage of subjects with threshold < 2.5 V in Vector 1 and at least one nonstandard vector).

14. APPENDIX A: DEFINITION OF TERMS

Abnormal Defibrillation Impedance – Defibrillation impedance is typically considered abnormal if a measurement is $< 25 \Omega$ or $> 150 \Omega$ (based on lead model and measurement range of the device). Includes high or low shock impedance when attempting to deliver a shock.

Abnormal Pacing Impedance – Pacing impedance is typically considered abnormal if a measurement is $< 200 \Omega$ or $> 3000 \Omega$ (based on lead model and measurement range of the device).

Cardiac Perforation associated with a lead – Penetration of the lead tip through the myocardium (including microperforation), clinically suspected and confirmed by chest x-ray, fluoroscopy, echocardiogram, intracardiac electrogram and/or visually.

Clinical Lead Failure – Inability of the lead to correctly sense or pace in the heart, not attributable to a mechanical or electrical failure of the lead or pulse generator and that remains unresolved despite reprogramming and/or repositioning.

Coronary Sinus Dissection – A tear that occurs in the wall of the coronary sinus.

Electrical Lead Failure – Confirmed or suspected lead issue that is due to an electrical failure of the lead, such as electrical noise not attributable to other causes, and that leads to loss of pacing and/or sensing. Specific types of confirmed or suspected electrical lead failures, such as high impedance values, no capture, and loss of sensing, are separate adverse event categories and should only be reported once. Confirmed or suspected electrical lead failures caused by induced malfunctions, such as lead damage caused during a procedure, are excluded.

Elevated Pacing Threshold – Either of the following is considered an elevated pacing threshold for the Sentus QP lead:

- At implant: pacing threshold $> 3.0 \text{ V}$ at 0.4 ms or 0.5 ms
- At routine evaluation: pacing threshold $> 2.5 \text{ V}$ at 0.4 ms or 0.5 ms

These thresholds are less than half of the maximum output in BIOTRONIK CRT devices and allow for an adequate safety margin.

Extracardiac Stimulation – Clinical observation of inadvertent nerve/muscle stimulation other than cardiac muscle, such as phrenic nerve stimulation.

Failure to Capture or Intermittent Capture – Intermittent or complete failure to achieve cardiac stimulation at programmed output delivered outside of the cardiac refractory period. This will be considered an AE if invasive intervention is taken. In absence of invasive intervention, this will only be considered an AE if there is failure to capture at the permanently programmed output with a minimum 2:1 safety margin. Sudden and significant increase in the pacing threshold value (elevated threshold compared to previous measured value) at which 2:1 safety margin can no longer be achieved.

Failure to Sense or Undersensing – Intermittent or complete loss of sensing or failure to detect intended intrinsic cardiac signals (atrial or ventricular) during non-refractory periods at programmed sensitivity settings. In absence of additional invasive intervention, this will only be considered an AE if the loss of sensing is not due to a medical reason and cannot be resolved with reprogramming.

Hematoma – A localized collection of extravasated blood, usually clotted, in an organ, space, or tissue. A hematoma is not considered a protocol defined AE unless it is a major hematoma related to the implant procedure. See major hematoma.

High Pacing Threshold – High lead pacing threshold resulting in invasive intervention. In absence of invasive intervention, at follow-up, lead threshold that has increased two fold from the chronic threshold value, and is unable to achieve a 2:1 safety margin.

Incorrect Lead/Header Connection – Lead connector pin connected to wrong header port, such as swapping leads or reversing connector pins, that is not identified and corrected prior to the end of the implant/revision procedure.

Infection – An invasion and multiplication of microorganisms in body tissues causing local cellular injury and requiring intravenous antibiotics and or system removal/extraction.

Lead Conductor Fracture – A mechanical break within the lead conductor (includes connectors, coils and / or electrodes) observed visually, electrically, or radiographically.

Lead Dislodgment – Radiographic, electrical or electrocardiographic evidence of electrode displacement from the original implant site or electrode displacement that adversely affects pacing, and/or lead performance.

Lead Explant – Surgical removal of a lead either by simple traction (such as occurs during the acute implant stage) or using manipulation and tools (as can be required for chronically implanted leads).

Lead Insulation Breach or Insulation Break – A disruption or break in lead insulation observed visually, electrically, or radiographically.

Loose Set Screw – Header set screw not properly tightened prior to end of implant/revision procedure.

Major Hematoma – Hematoma requiring evacuation, drainage, blood transfusion, hospitalization or extension of hospital stay to treat hematoma.

Mechanical Failure – Malfunction of the lead through a break in the conductor, insulation, or connector pin leading to loss of pacing / sensing observed visually, electrically, or radiographically. Confirmed or suspected mechanical failures induced by intervention, such as lead damage caused during a procedure, are not protocol defined adverse events.

New York Heart Association (NYHA) Functional Classification – A recognized system of classifying the extent of heart failure.

NYHA Class	Symptoms
I	Subjects with cardiac disease, but without resulting limitation of physical activity. Ordinary physical activity does not cause undue fatigue, palpitation, dyspnea, or anginal pain.
II	Subjects with cardiac disease resulting in slight limitation of physical activity. They are comfortable at rest. Ordinary physical activity results in fatigue, palpitation, dyspnea, or anginal pain.
III	Subjects with cardiac disease resulting in marked limitation of physical activity. They are comfortable at rest. Less than ordinary activity causes fatigue, palpitation, dyspnea, or anginal pain.
IV	Subjects with cardiac disease resulting in inability to carry on any physical activity without discomfort. Symptoms of cardiac insufficiency or of anginal syndrome may be present even at rest. If any physical activity is undertaken, discomfort is increased.

Non-healing Pocket Dehiscence – Separation of wound edges around the pocket of the implanted pulse generator that have not healed.

Pneumothorax – Air or fluid in the pleural space surrounding the lung leading to collapse or partial collapse of the lung requiring observation or chest tube placement

Premature Battery Depletion – Reaching elective replacement indicator (ERI) before the predicted date.

Pulmonary Embolism – Blockage of the main artery of the lung or one of its branches by a substance that has travelled from elsewhere in the body through the bloodstream.

Pulse Generator Failure – Confirmed or suspected pulse generator issue that is due to a mechanical failure or electrical malfunction, such as inability to communicate with pulse generator, electrical circuit failure, or inability to deliver therapy, that is not attributable to another component of the system or caused by an external source.

Skin Erosion – Deterioration of tissue over an implanted device or the movement of a lead toward or through the skin.

Tamponade – Compression of the heart caused by blood accumulation in the space between the myocardium and the pericardium.

Thrombosis – The development of a blood clot in a vein or artery that leads to the obstruction of blood flow.

Twiddler's Syndrome – A condition where the pulse generator leads are dislodged by the subject unwittingly rotating or otherwise moving the subcutaneous pulse generator.

Venous Occlusion – Blockage of a vein causing a reduction of blood supply and associated symptoms.

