5. STUDY OVERSIGHT

5.1 Clinical Events Committee

A Clinical Events Committee (CEC) consisting of at least 3 independent Electrophysiologists or Cardiologists (with CRT experience) will be established to review and adjudicate all protocol defined adverse events reported by the investigational sites related to:

1. Lead or generator adverse event resolved by surgical reposition, surgical explanation, surgical replacement, surgical abandonment, or if other lead-related surgery is performed
2. Adverse event related to clinical lead failure, electrical lead failure, or mechanical lead failure, regardless of action taken. This includes PNS resolved by electrical abandonment and disabled pacing
3. Any major implant procedure related event that meets the criteria of a serious adverse event
4. (MPP Sub-Study Only, see Section 11.3.4) MPP sub-study related events.

Protocol defined adverse events that do not meet these criteria for CEC adjudication (e.g. reprogramming pacing output due to high LV threshold without a suspected or confirmed lead failure) will be included in the clinical report based on site-reported information.

The CEC will be blinded to the investigational site and subject identity, and to minimize bias members will not participate as investigators. The CEC will create a study specific charter defining the adverse event adjudication process, specifically detailing review guidelines along with appropriate response timelines.

Adverse events meeting the criteria described above will be adjudicated by the Clinical Events Committee. The Clinical Events Committee (CEC) will have the responsibility to adjudicate the classification, category, seriousness, and resolution of each reported adverse event. In addition, the CEC will also indicate whether the adverse event is related, possibly related, not related, or has an unknown relation to the Sentus QP lead or Plexa ICD lead. The CEC will decide for each event on the inclusion to the primary endpoint 3 analysis according to the definition for endpoint 3 relevant adverse events as documented in Section 6.6.2.

The Clinical Events Committee is responsible for:

- Endpoint adjudication of adverse events meeting the criteria above
- Adjudication meetings, as needed, via telephone conference or face-to-face
- Final decision on inclusion of each adverse event in the primary endpoint 3 analysis according to the definition provided in Section 6.6.2.
- Regular reporting of adjudication results to the sponsor

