In addition, the following procedure-related adverse events will be included in the analysis of primary endpoint 1:

- Pneumothorax directly associated with the Sentus QP lead

- Cardiac perforation with or without tamponade caused by the Sentus QP lead
- Coronary sinus dissections directly caused by the Sentus QP lead (e.g., dissections caused by lead delivery device are excluded)

Finally, subject deaths resulting from a Sentus QP lead-related AE will be included in the primary endpoint analysis.

6.6.2 Adverse Events Included in Primary Endpoint 3

ADEs related to the Sentus QP lead and resolution combinations that will be analyzed as part of the primary endpoint 3 ($p_{\text{Complication}}^{\text{SentusQP}}$) are presented in Table 8. Combinations marked with an “X” will be included but are not limited to the primary endpoint 3 analysis. All Sentus QP related ADEs meeting the below criteria occurring after successful implantation until the 60-month post-implantation visit will be included.

Table 8: Adverse Event/Resolution Combinations for Primary Endpoint 3 Analysis

Resolution	Clinical lead failure	Electrical lead failure	High pacing threshold excluding events within 45 days of implant or lead revision	Extracardiac stimulation	Intermittent capture excluding events within 45 days of implant or lead revision	Lead dislodgement >45 days post-implant or lead revision	Lead impedance out of range, high	Lead impedance out of range, low	Lead undersensing	Lead-related thrombosis	Loss of sensing	Mechanical lead failure	No capture excluding events within 45 days of implant or lead revision
Lead surgically repositioned	X	X	X	X	X	X	X	X	X	X	X	X	X
Lead surgically explanted	X	X	X	X	X	X	X	X	X	X	X	X	X
Lead surgically replaced	X	X	X	X	X	X	X	X	X	X	X	X	X
Lead surgically abandoned	X	X	X	X	X	X	X	X	X	X	X	X	X
Other lead-related surgery performed	X	X	X	X	X	X	X	X	X	X	X	X	X
Lead pacing polarity or mode reprogrammed*		X										X	
Lead electrically abandoned and pacing disabled	X	X										X	
Lead use continued based on medical judgment	X	X										X	

*Adverse events resolved by reprogramming of pacing polarity or pacing mode are only included in primary endpoint 3 analysis in cases of electrical or mechanical lead failure. Other adverse events, such as extracardiac stimulation, which are resolved by reprogramming are excluded.

In addition, the following adverse events will be included in the analysis of primary endpoint 3:

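### A suspected electrical lead failure managed without surgery can drop out of primary endpoint 3 because of the sign under which it is coded

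*Combined protocol and SAP*

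**What the plan says.** All references are to the combined protocol and SAP.

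- **Appendix A, Electrical Lead Failure.** The entry begins "Confirmed or suspected lead issue that is due to an electrical failure of the lead" and requires loss of pacing and/or sensing. It then says that specific types of confirmed or suspected failure, "such as high impedance values, no capture, and loss of sensing, are separate adverse event categories and should only be reported once".
- **Section 6.6.2, Table 8.** The five surgical rows are marked for every category. The row "Lead pacing polarity or mode reprogrammed" is marked only for Electrical and Mechanical lead failure. The row "Lead electrically abandoned and pacing disabled" and the continued-use row are marked only for Clinical, Electrical and Mechanical lead failure. High impedance, no capture and loss of sensing have no mark in any of these three rows.
- **Table 8 footnote.** Events resolved by reprogramming polarity or mode "are only included in primary endpoint 3 analysis in cases of electrical or mechanical lead failure"; other events resolved that way are excluded.
- **Section 5.1.** The second intake criterion of the Clinical Events Committee (CEC) is "Adverse event related to clinical lead failure, electrical lead failure, or mechanical lead failure, regardless of action taken". The CEC adjudicates category and makes the final decision on inclusion in endpoint 3.
- **Section 12.2, Table 13 footnote.** The predecessor-lead registry counted a lead-related event "when polarity or mode reprogramming was utilized for suspected lead failures".

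**The concern.** Table 8 and Section 5.1 share an intention: a failure of the lead itself is a complication whether or not the patient goes back to surgery. Appendix A works against this. It takes three typical electrical signs of such a failure and makes them categories of their own, and Table 8 gives those categories no credit without surgery. Two leads with the same kind of fault, managed in the same way, can then be scored differently.

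Endpoint 3 is the five-year safety claim. The lead offers 12 pacing vectors (Section 1.3.2), so programming around a faulty pole is feasible, and any omission falls where this design makes surgery avoidable. The error can only raise the reported complication-free rate. Secondary endpoints 7 and 8 use the same event definitions, and the Kaplan-Meier curve of Section 2.3.7, which triggers reporting to FDA, follows the same outcome. Table 7 for endpoint 1 has the same structure, but that analysis is complete.

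**Working it through.** **Step 1. Follow one fault through the rules.** Take a suspected electrical failure with loss of pacing, no conductor, insulation or connector break established, and no surgery.

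| Presenting sign | Category on the natural reading of Appendix A | Reprogrammed | Electrically abandoned | Use continued |
|---|---|---|---|---|
| Electrical noise with no other cause | Electrical lead failure | counted | counted | counted |
| Impedance above 3000 Ohms | Lead impedance out of range, high | not marked | not marked | not marked |
| No capture | No capture | not marked | not marked | not marked |

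Loss of sensing has the same blank cells and a further obstacle. Under the Appendix A entry for failure to sense or undersensing, without invasive intervention it is an adverse event only if reprogramming cannot resolve it. A case that reprogramming resolves may never be reported.

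**Step 2. Reproduce the plan's sample size.** Inputs from Section 2.4.2: goal p0 = 0.925, expected p1 = 0.9475, one-sided alpha 0.025, power 80%, attrition 11% per year.

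- Normal approximation: n = [(1.960 × √(0.925 × 0.075) + 0.842 × √(0.9475 × 0.0525)) / 0.0225]² = 978.8, so 979. This matches the plan.
- Enrolment: 979 / 0.89⁵ = 1753.2, so 1754. This matches the plan.

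The sample size is sound on its own inputs; the issue is what counts as an event.

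**Step 3. Find the pass mark.** Section 2.3.4 requires the exact lower bound (two-sided 95%) to exceed 92.5%.

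- 57 failures: 922/979, lower bound 92.52%, passes.
- 58 failures: 921/979, lower bound 92.41%, fails.
- Exact alpha at this cutoff is 2.4% and power is 81.1%.
- Expected failures at 94.75%: 979 × 0.0525 = 51.4. The margin is 57 − 51.4, about 6 subjects.

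**Step 4. Illustrate sensitivity.** Let u be the share of subjects whose only event is an uncounted lead failure. The documents do not give u; the values below are assumptions. With a true complication-free rate of 92.5%, the counted failure rate is 7.5% − u, and the chance of passing is P(X ≤ 57) for X ~ Binomial(979, 7.5% − u).

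| u (assumed) | Subjects (979 × u) | Chance of passing |
|---|---|---|
| 0 | 0 | 2.4% |
| 0.25% | about 2 | 4.5% |
| 0.5% | about 5 | 8.1% |

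This is an inflation of error only if the 92.5% goal is meant to cover these events.

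**The case against.** **Appendix A does not name the category to use.** A reader might infer that it requires such events to be filed under the specific sign. It says only that the types are separate categories, reported once, which could be no more than a bar on double reporting. This stands: filing under the sign is the natural reading, not a stated rule.

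**Many conductor faults are already covered.** A reader might infer that any single-conductor fault programmed around is lost. That goes too far. Appendix A defines Mechanical Failure to include a break in conductor, insulation or connector pin that is detected electrically and leads to loss of pacing or sensing. That column is marked in all three non-surgical rows, and nothing moves such events out of it. What remains is the suspected electrical fault with no established break.

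**There are safeguards.** The CEC decides category and inclusion. Section 6.6.2 says the marked combinations are not exhaustive. The footnote governs reprogramming only, not abandonment or continued use, and its reference to lead failure could be read as cause rather than coded label. Section 5.1 itself gives, as an event outside adjudication, reprogramming for high threshold when no lead failure is suspected, which suggests that suspicion cuts across signs. All this gives the CEC room to count these events. None of it tells the CEC to do so, and the CEC would be applying the same Appendix A definitions. An event coded by sign and reprogrammed may not be sent to the CEC at all, because events outside the intake criteria stay as the site reported them.

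**The size has no anchor.** Larger assumed shares give striking figures (21.5% at 1.0%, 44.1% at 1.5%), and a reader might infer serious inflation. The documents do not support those shares. The nearest figure is in Table 13: 1 of 2,128 registry subjects, 0.05%, with out-of-range impedance by 6 months. Multiplied by 10 to reach 5 years, on an unsupported assumption of constant risk, this is about 0.5% for all resolutions, surgical ones included. It covers only the impedance sign and a different lead. Nor does the pre-market high-impedance event in Table 2 show omission: it was counted. Finally, the documents do not derive the 92.5% goal, and Section 12 ties the registry to the pre-market endpoints, so the registry does not set the scope of endpoint 3.

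**Conclusion.** The concern holds in a limited form. Appendix A, Table 8 and its footnote do not fit together for a suspected electrical lead failure that shows as high impedance, no capture or loss of sensing, has no established break, and is managed without surgery. On the natural reading it can be left out of endpoint 3, contrary to the evident intention of Table 8 and Section 5.1. The existing safeguards narrow the gap but leave it to unstated discretion.

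The number of affected subjects cannot be estimated from the documents. What can be said is that the margin is about 6 subjects in 979, so a handful of uncounted events could change the result. The rise from 2.4% to 4.5% or 8.1% is illustrative and rests on three assumptions: the share u, a true rate exactly at the goal, and a goal that covers these events. A reader might infer that endpoint 3 is invalid; the documents do not show that. They show a definition to settle before the five-year data are read.

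**What to change.** 1. In Appendix A, Section 6.6.2 and the CEC charter, state that the CEC records confirmed or suspected electrical or mechanical lead failure as a cause attribute, whatever the presenting category. Events with this attribute count under the Electrical or Mechanical lead failure column for all resolutions. This is better than adding marks to Table 8 for every sign, which would also bring in events with no suspected lead failure.
2. In Section 5.1, send every event with a suspected lead failure to the CEC, whichever category the site chose.
3. Reconcile the Appendix A entry for failure to sense or undersensing, so that an event with a suspected lead failure is reportable even when reprogramming resolves it. Without this, the first change cannot reach loss of sensing.
4. Apply the same rule to secondary endpoints 7 and 8 and to the Section 2.3.7 Kaplan-Meier curve.

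The cost is a wording amendment, a charter update, some added adjudication, and a re-check of non-surgical events already reported under these signs. The complication-free rate may come out slightly lower. Timing is favourable: U.S. enrolment began in October 2015 and this version is dated February 2017, so no 60-month visit had taken place and the rule could be set prospectively.
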